6.7 IMMUNOGENICITY ANALYSES

Immunogenicity may be assessed for atezolizumab and other study treatments as appropriate (refer to arm-specific appendices for details). The immunogenicity analyses will include all patients with at least one anti-drug antibody (ADA) assessment. Patients will be grouped according to treatment received or, if no treatment is received prior to study discontinuation, according to treatment assigned.

For atezolizumab, the numbers and proportions of ADA-positive patients and ADA-negative patients at baseline (baseline prevalence) and after baseline (postbaseline incidence) will be summarized by treatment group. When determining postbaseline incidence, patients are considered to be ADA positive if they are ADA negative or are missing data at baseline but develop an ADA response following study drug exposure (treatment-induced ADA response), or if they are ADA positive at baseline and the titer of one or more postbaseline samples is at least 0.60 titer unit greater than the titer of the baseline sample (treatment-enhanced ADA response). Patients are considered to be ADA negative if they are ADA negative or are missing data at baseline and all postbaseline samples are negative, or if they are ADA positive at baseline but do not have any postbaseline samples with a titer that is at least 0.60 titer unit greater than the titer of the baseline sample (treatment unaffected).

For other study treatments for which ADAs are tested, positivity will be determined according to standard methods established for previous studies of these drugs.

The relationship between ADA status and safety, efficacy, PK, and biomarker endpoints may be analyzed and reported using descriptive statistics.

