ADA=anti-drug antibody; ASTCT=American Society for Transplantation and Cellular Therapy; CRS=cytokine release syndrome; DOR=duration of response; NCI CTCAE=National Cancer Institute Common Terminology Criteria for Adverse Events, Version 5.0; ORR=objective response rate; OS=overall survival; PFS=progression-free survival; PK=pharmacokinetic; RECIST v1.1=Response Evaluation Criteria in Solid Tumors, Version 1.1.

Note: Overall response at a single timepoint will be assessed by the investigator using RECIST v1.1 (see [Appendix 1](#)).

Table 2 Objectives and Corresponding Endpoints for Stage 1 (cont.)

Exploratory Pharmacokinetic Objectives	Corresponding Endpoints

 To characterize the PK profile of drugs that are administered as part of a treatment combination during Stage 1 	
 Plasma or serum concentrations of each drug (as appropriate) at specified timepoints

 To evaluate potential relationships between drug exposure during Stage 1 and the efficacy and safety of treatment combinations 	
 Relationship between plasma or serum concentrations or PK parameters for each drug (as appropriate on the basis of available data) and efficacy endpoints Relationship between plasma or serum concentrations or PK parameters for each drug (as appropriate on the basis of available data) and safety endpoints
Exploratory Immunogenicity Objectives	Corresponding Endpoints

 To evaluate the immune response to drugs that are administered as part of a treatment combination during Stage 1 	
 For drugs for which ADA formation is measured: presence of ADAs during the study relative to the presence of ADAs at baseline

 To evaluate potential effects of ADAs during Stage 1 	
 For drugs for which ADA formation is measured: relationship between ADA status and efficacy, safety, or PK endpoints
Biomarker Objective	Corresponding Endpoint

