Approximately 40-90 patients will be enrolled during Stage 1. Enrollment in the experimental arm will take place in two phases: a preliminary phase, followed by an expansion phase. For most arms, approximately 20 patients will be enrolled during the preliminary phase. If clinical activity is observed in the experimental arm during the preliminary phase, approximately 25 additional patients may be enrolled in that arm during the expansion phase. The Sponsor may decide to delay or suspend enrollment within a given treatment arm. If the experimental arm shows minimal clinical activity or unacceptable toxicity, then it will not undergo expansion. Additional patients may be enrolled to ensure balance across treatment arms with respect to demographic and baseline characteristics, including potential predictive biomarkers, to enable further subgroup analyses. New experimental arms may be added during the study by amending the protocol.

Patients in Stage 1 will be randomly assigned to experimental arms or the control arm, and the randomization ratio will depend on the number of experimental arms that are open for enrollment (e.g., if an arm is added or enrollment in an arm is suspended pending analysis of results from the preliminary phase), with the stipulation that the likelihood of being allocated to the control arm will be no more than 50%. The treatment regimen in the control arm may change with emerging data to reflect the evolving standard-of-care treatments; new control arm treatment will be updated by amending the protocol. Randomization will take into account arm-specific exclusion criteria. Patients will be ineligible for a specific arm if they meet any of the exclusion criteria outlined for that arm (see [Section 4.1.2](#)). Details on treatment assignment and randomization are provided in [Section 4.2](#).

[figure not shown]
Table 4 Stage 1 Treatment Regimens

Arm Name	Study Treatment ^a	Number of Patients		Appendix
		Preliminary Phase	Expansion Phase ^b	
Control (Atezo + CAPOX) ^c	Atezolizumab plus capecitabine plus oxaliplatin	Variable ^d		Appendix 7
Atezo + CAPOX + Tira	Atezolizumab plus capecitabine plus oxaliplatin plus tiragolumab	20	25	Appendix 8

Atezo = atezolizumab; CAPOX = capecitabine plus oxaliplatin; Tira = tiragolumab.

- ^a The Sponsor may decide to delay or suspend enrollment within a given treatment arm. Thus, all listed experimental arms may not be open for enrollment at the same time.

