6.1 DETERMINATION OF SAMPLE SIZE

This study is not designed to make explicit power and type I error considerations for a hypothesis test. Instead, this study is designed to obtain preliminary efficacy, safety, and PK data on immunotherapy-based treatment combinations when administered to patients with GC or GEJC. Cohort 1 will enroll patients with inoperable locally advanced, metastatic, or advanced GC or GEJC with adenocarcinoma confirmed as the predominant histology who have not received prior systemic therapy for advanced or metastatic disease.

Approximately 40-90 patients will be randomly allocated to the control and experimental arms during the study.

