Appendix 7: Study Details Specific to Atezo + CAPOX Arm (Control) (cont.)

Table 5 Schedule of Pharmacokinetic, Anti-Drug Antibody, and Blood Biomarker Samples for Atezo+CAPOX Arm

Visit	Time	Sample Type
Day 1 of Cycle 1	Prior to infusion	
 • Atezolizumab PK (serum) • Atezolizumab ADA (serum) • Biomarker (serum and blood) • Biomarker (plasma and WBC)^a
	30 (± 10) minutes after end of atezolizumab infusion	
 • Atezolizumab PK (serum)
Day 1 of Cycles 2, 3, 4, 8, 12, and 16	Prior to infusion	
 • Atezolizumab PK (serum) • Atezolizumab ADA (serum) • Biomarker (serum and blood) on Day 1 of Cycles 2 and 3 only
Treatment discontinuation visit (≤ 30 days after final dose)	At visit	
 • Atezolizumab PK (serum) • Atezolizumab ADA (serum) • Biomarker (serum and blood) • Biomarker (plasma)^a

ADA=anti-drug antibody; Atezo=atezolizumab; CAPOX=capecitabine plus oxaliplatin; ctDNA=circulating tumor DNA; PK=pharmacokinetic; WES=whole exome sequencing.

Note: On the basis of emerging safety or efficacy data, the number of PK and ADA samples may be reduced or sample collection may cease altogether. Additionally, collected samples may not be analyzed if not warranted. Blood collections for biomarker assessment (e.g., cytokines, chemokines, gene expression profiling, ctDNA and WES of WBC-derived DNA as germline control) are applicable only after approval from local regulatory authorities. Based on emerging biomarker data, the number of biomarker samples may be reduced or sample collection may cease altogether.

^a Blood collected at site for central processing of plasma and WBC samples.

REFERENCES

- Bang Y-J, Hung H-C, Shakaran V, et al. Relationship between PD-L1 expression and clinical outcomes in patients with advanced gastric cancer treated with the anti-PD-1 monoclonal antibody pembrolizumab (MK-3475) in KEYNOTE-012. *J Clin Oncol* 2015;33(15 Suppl):4001–4001.

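### Under Section 6.7, any efficacy comparison by ADA status is biased towards ADA-positive patients, because status is ever-positive over sampling that stops with treatment

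*Combined protocol and SAP*

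**What the plan says.** Table 2 in Section 2 lists as an exploratory Stage 1 endpoint the "relationship between ADA status and efficacy, safety, or PK endpoints". Table 3 repeats it for Stage 2. Section 6.7 gives the analysis: "The relationship between ADA status and safety, efficacy, PK, and biomarker endpoints may be analyzed and reported using descriptive statistics".

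For atezolizumab, Section 6.7 calls a patient post-baseline positive after an induced response at any time, or after a sufficient titre rise in at least one later sample. A patient is negative only if no later sample qualifies. The rule is introduced for post-baseline incidence. Entry to the immunogenicity analyses needs one ADA assessment, not necessarily a post-baseline one. For other drugs, positivity follows methods from their earlier studies.

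In the control arm (Appendix 7, Table 5), post-baseline atezolizumab ADA samples are due on "Day 1 of Cycles 2, 3, 4, 8, 12, and 16" and at the treatment discontinuation visit. Appendix 8, Table 6 gives the same times for the tiragolumab arm. In both arms, Section 3.1.2 and the schedule footnotes continue treatment until unacceptable toxicity or loss of clinical benefit.

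**The concern.** The number of chances to be classed as positive depends on how long the patient stays on treatment, and that depends on outcome. A patient who stops around Week 6 has one or two scheduled samples plus the discontinuation visit. A patient still on treatment at Week 45 has had six. This is guarantee-time (immortal-time) bias: the positive group is enriched for patients who lasted long enough to be caught, even if ADAs do nothing.

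ORR is affected as well as PFS and OS. A confirmed response needs two assessments at least 4 weeks apart on a 6-weekly scan schedule, so early leavers tend to be both non-responders and ADA negative. Section 6.7 also leaves open that a patient with no post-baseline sample counts as negative.

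A descriptive table or Kaplan-Meier plot carries the bias just as a test would. If ADAs do reduce activity, the bias works against seeing it. The documents name no landmark, time-dependent covariate, restriction to early samples or adjustment for exposure.

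**Working it through.** **1. The plan's own figure.** Section 6.1 states: "Approximately 40-90 patients will be randomly allocated to the control and experimental arms during the study". Section 3.1.2 plans about 20 patients in the experimental arm, then about 25 more (45 in total), with control allocation of at most 50%. At 1:1, 20/0.5 = 40 and 45/0.5 = 90, which reproduces the range. The documents give no figure for ADA incidence or onset, so the size below rests on assumptions.

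**2. Sampling times.** With 21-day cycles, Day 1 of Cycle c falls at week 3(c − 1): weeks 3, 6, 9, 21, 33 and 45 for Cycles 2, 3, 4, 8, 12 and 16.

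**3. Null simulation for PFS and ORR** (6,000 patients per scenario; true HR 1).
- From the documents: the sampling weeks; a discontinuation sample 0–30 days after treatment stops; and median PFS of 6 months (low end for CAPOX, Section A7–1.2) or 7.7 months (nivolumab plus chemotherapy, CPS ≥ 5, Section 1.2).
- Assumed: exponential PFS; treatment stops at progression; 20%, 30% or 40% develop ADA by week 48; onset independent of PFS and early (time constant 3 weeks), middle (10 weeks) or uniform over 48 weeks; response possible only if PFS exceeds 10 weeks, then with probability 0.7.
- Comparison: Cox HR for ever-positive versus never-positive, then the same with status fixed at Week 9 in patients still progression-free.

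Ranges over the six scenarios for each onset pattern:

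| Onset | HR, ever vs never | ORR gap, positive minus negative (points) | HR, Week 9 landmark | ADA positive at landmark |
|---|---|---|---|---|
| Early | 0.93–0.96 | −1 to +4 | 0.97–1.01 | 18.5–37.6% |
| Middle | 0.78–0.90 | +6 to +13 | 0.94–1.08 | 11.9–25.5% |
| Uniform to week 48 | 0.60–0.69 | +10 to +16 | 0.91–1.09 | 3.7–7.8% |

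The ever/never HR is below 1 in all 18 scenarios. At a 7.7-month median and 30% incidence, median PFS is 9.5 vs 7.0 months with middle onset and 11.9 vs 6.7 months with uniform onset. The landmark HRs scatter around 1, most widely where few patients are positive. OS was not simulated; the mechanism is the same, but no size is claimed.

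**4. Treatment beyond progression.** In a separate null run with a discontinuation sample 2 weeks after progression, ORR gaps were 4–15 points. Adding a mean of 12 weeks' treatment beyond progression for everyone (assumed, and generous) cut them to 1–8 points.

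**5. Prognostic confounding.** Half the patients were given a worse prognosis and a higher ADA risk, still with no ADA effect (7.7 months; early and middle onset):
- prognosis HR 1.5, ADA risk 25% vs 35%: observed HR 0.95 and 0.82;
- HR 2, 20% vs 40%: 1.09 and 0.91;
- HR 2.5, 15% vs 45%: 1.26 and 1.04.

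**6. Trial size** (7.7 months, 30%, middle onset, true HR 1): median HR 0.84 at N = 40 (95% range 0.41–1.54) and 0.85 at N = 90 (0.52–1.40).

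**The case against.** The strongest reply is that the plan never commits to this analysis. The any-sample rule is introduced for incidence, the efficacy sentence does not say which ADA status it means, and the relationship only *may* be analysed. The appendix tables allow ADA sampling to be cut back or samples left unanalysed. On the study as a whole, Section 6.1 says: "This study is not designed to make explicit power and type I error considerations for a hypothesis test". With 40–90 patients, step 6 shows sampling noise wider than the bias. The inputs that set its size are assumed, and with early onset it is small.

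Much of that stands, and it rules out some readings that a reader might infer. The documents do not show that ADA-positive patients will look better: step 5 shows that confounding can push the observed HR above 1. They do not show a bias of any particular size. They also do not frame the endpoint as a test of whether ADAs reduce efficacy; Table 2 names only a relationship.

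Treatment beyond RECIST progression (Sections 3.1.2 and 3.3.2) loosens the link between PFS and sampling but does not break it, since sampling still ends with treatment. The synopsis (Duration of Participation) instead runs treatment to RECIST progression. These passages must be reconciled, because the size of the bias depends on which applies.

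What does not stand is the appeal to incidence. Section 6.7 defines no other post-baseline status for atezolizumab, so an analyst following it would use the ever-positive one. Nor does small N help: noise hides the bias in one trial, but more patients or pooling would not remove it.

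**Conclusion.** The concern holds as a flaw in an optional, exploratory, descriptive analysis. The only post-baseline ADA status that Section 6.7 defines for atezolizumab, related to efficacy, is biased towards ADA-positive patients and could mask a real loss of activity. Under the null, the PFS HR is about 0.93–0.96 if ADAs appear early and 0.60–0.90 if later. This assumes 20–40% incidence, exponential PFS with a median of 6 or 7.7 months, and treatment ending at progression. It is smaller if treatment continues beyond progression, and prognostic confounding can offset or reverse the observed direction.

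A reader might infer that the trial's efficacy result is compromised. It is not: the primary ORR comparison is between arms and does not use ADA status.

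**What to change.** In Section 6.7, keep the ever-positive rule for reporting incidence. Add that, if ADA status is related to efficacy, one of these will be used:

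- **Landmark.** Take status from samples up to a prespecified time, for example Cycle 4 Day 1 (Week 9), in patients still event-free with at least one post-baseline ADA sample. Count PFS and OS from the landmark. Use Cycle 3 Day 1 (Week 6) as sensitivity. Week 6 is less suitable as the main choice because it coincides with the first scan, so event-free status could turn on which came first. Since scans ignore dose delays and ADA samples follow cycles, say whether the week or the visit governs.
- **Time-dependent covariate.** Enter ADA status this way for PFS and OS. It keeps late converters but does not serve ORR.

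The cost is wording, with no new samples. Patients who progress or leave before the landmark drop out of this comparison. With exponential PFS and 4.345 weeks per month, the share is 1 − 2^(−(9/4.345)/m): 17% at m = 7.7 months and 21% at m = 6. For Week 6 it is 12% and 15%.

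Late converters count as negative under the landmark, and few positives may remain. With uniform onset and N = 90, 90 × 0.787 × 0.037 ≈ 3 to 90 × 0.830 × 0.077 ≈ 6 ADA-positive patients; with N = 40, about 1 to 3. The landmark does not adjust for prognosis, so the text should call the results descriptive and unadjusted.

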6.8 BIOMARKER ANALYSES

Biomarker analyses will be performed in an effort to understand the association of these biomarkers with response to study drugs, taking into account efficacy and safety endpoints (see Section 4.5.7 for more details).

6.9 INTERIM ANALYSES

[REDACTED]

[REDACTED]

7. DATA COLLECTION AND MANAGEMENT

7.1 DATA QUALITY ASSURANCE

The Sponsor will be responsible for data management of this study, including quality checking of the data. Data entered manually will be collected via EDC through use of eCRFs. Sites will be responsible for data entry into the EDC system. In the event of discrepant data, the Sponsor will request data clarification from the sites, which the sites will resolve electronically in the EDC system.

The Sponsor will produce an EDC Study Specification document that describes the quality checking to be performed on the data. Central laboratory data will be sent directly to the Sponsor, using the Sponsor's standard procedures to handle and process the electronic transfer of these data.

eCRFs and correction documentation will be maintained in the EDC system's audit trail. System backups for data stored by the Sponsor and records retention for the study data will be consistent with the Sponsor's standard procedures.

7.2 ELECTRONIC CASE REPORT FORMS

eCRFs are to be completed through use of a Sponsor-designated EDC system. Sites will receive training and have access to a manual for appropriate eCRF completion. eCRFs will be submitted electronically to the Sponsor and should be handled in accordance with instructions from the Sponsor.

All eCRFs should be completed by designated, trained site staff. eCRFs should be reviewed and electronically signed and dated by the investigator or a designee.

At the end of the study, the investigator will receive patient data for his or her site in a readable format on a compact disc that must be kept with the study records. Acknowledgement of receipt of the compact disc is required.

7.3 SOURCE DATA DOCUMENTATION

Study monitors will perform ongoing source data verification and review to confirm that critical protocol data (i.e., source data) entered on the eCRFs by authorized site personnel are accurate, complete, and verifiable from source documents.

Source documents (paper or electronic) are those in which patient data are recorded and documented for the first time. They include, but are not limited to, hospital records, clinical and office charts, laboratory notes, memoranda, evaluation checklists, pharmacy dispensing records, recorded data from automated instruments, copies of transcriptions

that are certified after verification as being accurate and complete, microfiche, photographic negatives, microfilm or magnetic media, X-rays, patient files, and records kept at pharmacies, laboratories, and medico-technical departments involved in a clinical trial.

Before study initiation, the types of source documents that are to be generated will be clearly defined in the Trial Monitoring Plan. This includes any protocol data to be entered directly on the eCRFs (i.e., no prior written or electronic record of the data) and considered source data.

Source documents that are required to verify the validity and completeness of data entered on the eCRFs must not be obliterated or destroyed and must be retained per the policy for retention of records described in Section 7.5.

To facilitate source data verification and review, the investigators and institutions must provide the Sponsor direct access to applicable source documents and reports for trial-related monitoring, Sponsor audits, and IRB/EC review. The study site must also allow inspection by applicable health authorities.

7.4 USE OF COMPUTERIZED SYSTEMS

When clinical observations are entered directly into a study site's computerized medical record system (i.e., in lieu of original hardcopy records), the electronic record can serve as the source document if the system has been validated in accordance with health authority requirements pertaining to computerized systems used in clinical research. An acceptable computerized data collection system allows preservation of the original entry of data. If original data are modified, the system should maintain a viewable audit trail that shows the original data as well as the reason for the change, name of the person making the change, and date of the change.

7.5 RETENTION OF RECORDS

Records and documents pertaining to the conduct of this study and the distribution of IMPs, including eCRFs, Informed Consent Forms, laboratory test results, and medication inventory records, must be retained by the Principal Investigator for at least 15 years after completion or discontinuation of the study or for the length of time required by relevant national or local health authorities, whichever is longer. After that period of time, the documents may be destroyed, subject to local regulations.

No records may be disposed of without the written approval of the Sponsor. Written notification should be provided to the Sponsor prior to transferring any records to another party or moving them to another location.

Roche will retain study data for 25 years after the final Clinical Study Report has been completed or for the length of time required by relevant national or local health authorities, whichever is longer.

8. ETHICAL CONSIDERATIONS

8.1 COMPLIANCE WITH LAWS AND REGULATIONS

This study will be conducted in full conformance with the ICH E6 guideline for Good Clinical Practice and the principles of the Declaration of Helsinki, or the laws and regulations of the country in which the research is conducted, whichever affords the greater protection to the individual. The study will comply with the requirements of the ICH E2A guideline (Clinical Safety Data Management: Definitions and Standards for Expedited Reporting).

8.2 INFORMED CONSENT

The Sponsor's sample Informed Consent Forms (and ancillary sample Informed Consent Forms such as a Mobile Nursing Informed Consent Form, if applicable) will be provided to each site. If applicable, they will be provided in a certified translation into the local language. The Sponsor or its designee must review and approve any proposed deviations from the Sponsor's sample Informed Consent Forms or any alternate consent forms proposed by the site (collectively, the "Consent Forms") before IRB/EC submission. The final IRB/EC-approved Consent Forms must be provided to the Sponsor for health authority submission purposes according to local requirements.

If applicable, the Informed Consent Form will contain separate sections for any optional procedures. The investigator or authorized designee will explain to each patient the objectives, methods, and potential risks associated with each optional procedure. Patients will be told that they are free to refuse to participate and may withdraw their consent at any time for any reason. A separate, specific signature will be required to document a patient's agreement to participate in optional procedures. Patients who decline to participate will not provide a separate signature.

The Consent Forms must be signed and dated by the patient or the patient's legally authorized representative before his or her participation in the study. The case history or clinical records for each patient shall document the informed consent process and that written informed consent was obtained prior to participation in the study.

The Consent Forms should be revised whenever there are changes to study procedures or when new information becomes available that may affect the willingness of the patient to participate. The final revised IRB/EC-approved Consent Forms must be provided to the Sponsor for health authority submission purposes.

If the Consent Forms are revised (through an amendment or an addendum) while a patient is participating in the study, the patient or a legally authorized representative must re-consent by signing the most current version of the Consent Forms or the addendum, in accordance with applicable laws and IRB/EC policy. For any updated or revised Consent Forms, the case history or clinical records for each patient shall document the informed consent process and that written informed consent was obtained using the updated/revised Consent Forms for continued participation in the study.

A copy of each signed Consent Form must be provided to the patient or the patient's legally authorized representative. All signed and dated Consent Forms must remain in each patient's study file or in the site file and must be available for verification by study monitors at any time.

